**Sponsor or funding source:** Departmental**BACKGROUND**

Chemodenervation of the bladder with onabotulinum toxin A is an effective treatment option for patients with refractory overactive bladder (OAB) or urgency urinary incontinence (UUI). It is often performed as an office-based procedure under local anesthesia. Alternatively, it can be performed in the operating room under general anesthesia. The ability to receive intra-detrusor chemodenervation in the office allows patients to avoid the risks associated with general anesthesia and is significantly more cost effective. The procedure, however, is painful and can be anxiety provoking for patients; especially given that patients typically return every six to nine months for repeat injections.

Relaxation and distraction techniques are one way to ease patients' anxiety before an office-based procedure. Aromatherapy and music have been shown to reduce anxiety and pain during procedures such as intravenous line placement, bone marrow biopsy, and cystoscopy. In the urogynecologic population, both lavender aromatherapy and listening to music during multi-channel urodynamics decreased patient anxiety and improved satisfaction. There have not, however, been any studies evaluating the use of aromatherapy or music during intra-detrusor chemodenervation procedures.

While we do not know exactly how anxiety provoking office bladder chemodenervation is for patients, we do know that anxiety disorders are highly prevalent in women with overactive bladder as a population. One study of 274 women with OAB found that 62.4% had moderate to severe anxiety. Addressing pre-procedural anxiety is important so patients will continue to pursue treatment of their OAB/UUI in the outpatient environment. Achieving a relaxing office environment with simple adjustments to aroma, music, and lighting may be one way to help patients feel less anxious, reduce the perception of procedural pain, and increase satisfaction with their procedural experience.

## **STUDY PURPOSE**

This study aims to investigate whether women with OAB/UUI who receive office intra-detrusor chemodenervation injections performed in a relaxing environment of lavender aromatherapy, calming music, dim lighting, and modest positioning (Relaxing Environment Package) will have decreased anxiety and pain as well as increased post-procedure satisfaction compared to patients who receive chemodenervation in a typical office environment. We will also investigate whether exposure to the relaxing environment impacts the well-being of staff involved in these procedures.

## **STUDY OBJECTIVES**

### **Primary Objective**

Determine if women with OAB/UUI exposed to a Relaxing Environment Package during office administration of intra-detrusor onabotulinum toxin A injections have decreased pre-procedure anxiety based on a visual analog scale compared to women receiving intra-detrusor onabotulinum toxin A injections performed in a typical office setting.

### **Secondary Objectives**

1. Determine if the Relaxing Environment Package reduces a patient's pain during office administration of intra-detrusor onabotulinum toxin A injections based on a visual analog scale.
2. Determine if the Relaxing Environment Package increases patient satisfaction with their procedure experience based on a visual analog scale.
3. Determine if the Relaxing Environment Package decreases procedure staff burnout based on a visual analog scale.

## **HYPOTHESIS**

We hypothesize that patients who experience a relaxing environment of lavender aromatherapy, calming music, dim lighting, and modest positioning during office intra-detrusor chemodenervation procedures will have less pre-procedure anxiety, less pain during the procedure, and greater procedure satisfaction compared to patients who experience a typical office setting. We additionally hypothesize that staff who are exposed to the relaxing environment will experience less burnout.

## **METHODS and MEASURES**

### **Design and Setting**

This is a single center prospective randomized controlled trial of women with overactive bladder undergoing their first or repeat office intra-detrusor chemodenervation with onabotulinum toxin A. The trial will be performed in an academic medical center outpatient Urogynecology clinic (Women's Center for Pelvic Health (Mercy), Atrium Health, Charlotte, NC). Approval by the Atrium Health Institutional Review Board will be obtained before data collection.

### **Subject Selection Criteria**

Women scheduled for office intra-detrusor chemodenervation with onabotulinum toxin A for a diagnosis of overactive bladder (OAB), urinary urgency (UU), or urgency urinary incontinence (UUI) based on subjective or objective data will be identified and screened against inclusion and exclusion criteria. If potential subjects meet the requirements for the study, they will be eligible to be invited for participation. Subjects will be consented for study enrollment by physicians, fellow physicians, and/or a delegated study team member on the day of their procedure.

### **Inclusion Criteria**

- Non-pregnant females
- Age 18 years and older
- English as a primary language
- Scheduled for office intra-detrusor chemodenervation for diagnosis of OAB/UU/UUI
- Baseline visual analog scale for anxiety  $\geq 12\text{mm}$

### **Exclusion Criteria**

- Allergy to lavender oil
- Contraindication to intra-detrusor chemodenervation procedure as determined by the physician

### **Inclusion of Women and Minorities**

Women of all races and ethnicity who meet the above-described eligibility criteria are eligible for this study. All participants will be women.

### **Study Withdrawal**

Subjects may withdraw from the study at any point in time. Documentation of the reason for withdrawal will be captured in the data collection forms. There will be no risk to subjects that choose to withdraw.

### **Sample Size**

Our sample size calculation was based on a prior study within the urogynecologic population which showed a statistically significant reduction in VAS-anxiety when aromatherapy was used during multichannel urodynamics, a common urogynecologic office procedure. With a sample size of  $n=80$  we would have 80% power to detect a mean clinically important difference of 12mm out of 100mm on the anxiety visual analog scale assuming a standard deviation of 18.8 and p-value 0.05. As the intervention is delivered at the week level, if we reach  $n=80$  early in the week, we will plan to finish out the week and thus may reach a total sample size slightly greater than 80, increasing statistical power.

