#### **Group 2:** Control

- Non-aromatic (placebo) sticker on patient, procedure staff, MD lapel
- No music playing
- Overhead lights on
- Stirrups used

In order to create the least disruption to our clinical workflow, we propose randomizing the weeks of the study rather than randomizing participants. Permuted block randomization will be used such that a random sequence of blocks of 4 or 6 weeks (totaling to the number of weeks planned for the study) will be chosen. Within each block of 4 or 6 weeks, the weeks will be equally randomized to treatment or control. For example, within a four-week block, two of four weeks will be randomized treatment and two to control. Permuted block randomization will ensure that (i) prognostic factors (e.g., first-time vs. repeat patient) are balanced over the course of the study and (ii) seasonality is addressed (e.g., within summer, half of the weeks are control and half treatment). Each week of the study will be randomized to either Relaxing Environment Package or Typical Office Environment (control), rather than randomizing individual patients. On Monday of every week, an envelope will be opened to determine if it is a Relaxing Environment Package week or Control week. Randomization will be discussed in more detail below.

If the week is randomized to a *Relaxing Environment Package*, the patient, procedure staff, and MD will enter the procedure room and receive a lavender aromatherapy sticker to be worn on their lapels. The lavender aromatherapy sticker will be ordered from Aroma Stickers store website (<https://aroma-stickers.com>). Calming music from Sirius XM station 68 (Spa) will be playing softly in the background via overhead speakers. If the patient had planned to listen to their own music during the procedure, this will be permitted and documented. Procedure consent and preprocedural preparation (see below) will take place. The overhead lights will then be turned off, and two battery powered lanterns will be lit to provide dim lighting. Stirrups will be avoided, if possible, during the preparation and procedure.

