## RANDOMIZATION

A permuted block randomization scheme will be used to assign weeks in a 1:1 ratio to intervention or control. The permuted blocks will prevent clinic staff from being able to predict which weeks will be Relaxing Environment Package or control. However, it will not be possible to blind subjects, staff, or investigators. Our statistician will be blinded. Randomization of weeks rather than patients was selected to minimize impact to clinic flow and help prevent protocol deviation among our busy clinic staff who often have back-to-back procedures. It will also allow assessment of procedure team burnout. Patients will only participate in the study once.

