## ANALYTICAL PLAN

Descriptive statistics will be used to summarize baseline characteristics of treatment and control groups. Means and standard deviations (or medians and interquartile ranges) will be used to summarize continuous variables such as age, and frequencies and percentages will be used to summarize categorical variables such as first-time vs. repeat patient. Regression analyses will be performed to test the hypotheses about treatment effects on primary and secondary outcomes. Planned regression models can flexibly address missing data and include covariate adjustment for important prognostic variables (such as first-time vs. repeat patient), as necessary. Exploratory subgroup analyses will be performed to characterize treatment effects within groups of interest, such as first-time or repeat patients.

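### Weeks are randomised, but the 80% power at n=80 assumes independent patients and the analysis plan does not commit to accounting for week

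*Combined protocol and SAP*

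**What the plan says.** The unit of randomisation is clear. Under the description of the control group the protocol says "we propose randomizing the weeks of the study rather than randomizing participants", and the Randomization section repeats it: "A permuted block randomization scheme will be used to assign weeks in a 1:1 ratio to intervention or control". Blocks are of 4 or 6 weeks, "totaling to the number of weeks planned for the study", but that number appears nowhere.

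The Sample Size section claims "80% power to detect a mean clinically important difference of 12mm out of 100mm on the anxiety visual analog scale" at n=80, with SD 18.8 and a p-value of 0.05. It recognises that delivery is by week, but uses this only to let enrolment run to the end of the last week, so that the trial "thus may reach a total sample size slightly greater than 80, increasing statistical power".

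The Analytical Plan says "Regression analyses will be performed to test the hypotheses about treatment effects on primary and secondary outcomes". On the form of the model it adds "Planned regression models can flexibly address missing data and include covariate adjustment for important prognostic variables". It names no week effect, mixed model, GEE, cluster-robust error or small-sample correction.

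**The concern.** When weeks are allocated, the independent replicates of the treatment are the weeks. Patients seen in one week may share a physician, nurses and clinic conditions that differ from other weeks. If their outcomes are positively correlated, 80 patients carry less information than 80 independent ones, and the treatment contrast has only as many degrees of freedom as the weeks allow.

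Two things are at stake. If the final model ignores week and the ICC is positive, the confidence interval for the primary comparison is too narrow and the type I error exceeds 5%. If week is accounted for, the advertised power is not what the design delivers on its stated inputs. Because the plan leaves the choice open, it could also be made after the data are seen, and it can change the standard error and p-value of the primary test.

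**Working it through.** **1. Inputs from the Sample Size section.** Difference 12 mm, SD 18.8 mm, alpha 0.05 (taken as two-sided), total n = 80, taken as 40 per arm.

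**2. Reproducing the stated power.**
- Standard error = 18.8 × √(2/40) = 4.204 mm; noncentrality = 12/4.204 = 2.855.
- Noncentral t on 78 df, critical value 1.991: power 80.5%. With 39 per arm it is 79.5%.
- Normal approximation: 2 × (18.8 × (1.960 + 0.842)/12)² = 38.5 per arm.

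So n=80 is the independent-patient answer, with a design effect of 1 and almost no slack. Even under the more generous normal approximation, the largest design effect that keeps 80% is 40/38.5 = 1.04.

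**3. Allowing for week.** The weekly count m and the ICC are assumptions, because the documents give neither. With equal weeks:
- design effect = 1 + (m − 1) × ICC
- standard error = 4.204 × √(design effect)
- df = weeks − 2, with weeks = 80/m

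Worked case, m = 5 and ICC = 0.05: design effect = 1 + 4 × 0.05 = 1.20; standard error = 4.204 × √1.20 = 4.605; noncentrality = 12/4.605 = 2.606; 16 weeks give 14 df and a critical value of 2.145; power = 67.9%.

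Power at n=80, with no covariate adjustment:

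| Patients per week (weeks) | df used | ICC 0 | ICC 0.01 | ICC 0.05 | ICC 0.10 |
|---|---|---|---|---|---|
| 2 (40) | weeks − 2 = 38 | 79.4% | 79.0% | 77.5% | 75.6% |
| 2 (40) | 78 | 80.5% | 80.1% | 78.6% | 76.7% |
| 5 (16) | weeks − 2 = 14 | 75.6% | 74.0% | 67.9% | 61.2% |
| 5 (16) | 78 | 80.5% | 78.9% | 73.0% | 66.4% |
| 8 (10) | weeks − 2 = 8 | 70.6% | 67.7% | 57.8% | 48.6% |
| 8 (10) | 78 | 80.5% | 77.8% | 68.0% | 58.0% |

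The 78-df rows show the loss from correlation alone. The gap to the row above is the price of having few weeks.

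**4. Type I error if week is ignored.** Approximately 2 × [1 − Φ(1.960/√(design effect))]. At ICC 0.05 the design effects are 1.05, 1.20 and 1.35, giving 5.6%, 7.4% and 9.2% for 2, 5 and 8 per week.

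**5. Check by simulation.** 3,000 runs per setting, Poisson weekly counts, blocks of 4 or 6 weeks, enrolment stopping at the end of the week in which 80 is reached. Results at ICC 0.01 / 0.05 / 0.10:

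| Mean per week | Random intercept for week (REML), weeks − 2 df | Size-weighted week-level analysis |
|---|---|---|
| 2 | 76 / 75 / 72% | 80 / 77 / 74% |
| 5 | 71 / 64 / 61% | 75 / 68 / 64% |
| 8 | 64 / 55 / 47% | 70 / 59 / 50% |

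Type I error was 2.3% to 5.2% for the mixed model (conservative in places) and 4.7% to 6.7% for the week-level analysis. Ignoring week at ICC 0.05 gave 6.5%, 8.3% and 9.6% (Monte Carlo standard error about 0.5 points). These sit somewhat above the closed form, which assumes equal weeks and a normal reference.

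**6. Patients for 80% power.** Adding whole weeks and testing on weeks − 2 df, ICC 0.01 to 0.10: about 84 to 92 patients at 2 per week, 100 to 120 at 5, and 112 to 160 at 8.

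**7. Finishing the last week.** Take 8 weeks of 5 in one arm, with the last week going from 2 to 5 patients. A week of m patients contributes m/[1 + (m − 1) × ICC]. That arm's effective size rises from 31.1 to 33.3 at ICC 0.05 and from 26.8 to 28.6 at ICC 0.10, so the three extra patients are worth about 2.3 and 1.8.

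**The case against.** The best reply is that the loss may be small.

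- **Change score.** The primary outcome is change from a same-day baseline, so week effects common to both scores cancel. This is fair, and the ICC may be low. But the baseline is taken in a research office and the second score in the procedure room, so effects of the room or the team do not cancel.
- **Covariates.** The plan allows adjustment, and a baseline score is available. If covariates correlated 0.4 with the outcome (an assumption; residual variance × 0.84), power on weeks − 2 df would be 82.5% to 85.5% at 2 per week over the ICC range, and 81.0% at 5 per week with ICC 0.01. Even at a correlation of 0.5 it stays below 80% at 8 per week (60.2% to 79.7%) and at 5 per week with ICC 0.10 (73.6%). So power below 80% is a statement about the unadjusted inputs. Adjustment is planned only as needed, and it does not protect the type I error against week-level correlation that remains.
- **Degrees of freedom.** Much of the loss at 8 per week comes from the few weeks, as the 78-df rows show. That stands as a description, but the number of weeks is part of the design and is missing.
- **Extreme case.** Ten weeks would be about two blocks, which fits poorly with blocking to handle seasonality. The 48.6% corner is therefore the least plausible cell. The documents nevertheless do not fix a weekly count, and they mention back-to-back procedures.
- **Regression may include week.** True. The plan does not rule it out, but it does not commit to it either.
- **Extra patients increase power.** That sentence in the Sample Size section is correct; it lacks only the qualification that the gain is smaller within a week.

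**Conclusion.** The concern holds, and the power statement is wrong as written for this design. The 80% is an independent-patient figure. On the plan's own unadjusted inputs, the closed-form power on weeks − 2 df is below 80% in every case tried: from 79.4% (2 per week, ICC 0) down to 48.6% (8 per week, ICC 0.10). In the mild case of 2 per week and ICC 0.01 the cost is only about 1.5 points (80.5% to 79.0%).

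The more serious half is the Analytical Plan's silence on week, which leaves the primary test open to a type I error above 5%: about 5.6% to 9.2% by the closed form at ICC 0.05. The direction is certain if the ICC is positive. The size rests on assumed weekly counts and ICCs, equal patient numbers per arm and a two-sided test. The point should be settled before analysis because it bears on the validity of the primary comparison.

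**What to change.** 1. **Analytical Plan.** State that the patient outcomes (VAS anxiety, pain and satisfaction) are analysed with week as the cluster. One option is a linear mixed model with a random intercept for week and a small-sample degrees-of-freedom correction; a week-level analysis or small-sample-corrected cluster-robust errors would serve equally. A test that re-randomises weeks within the 4- and 6-week blocks is an optional supporting analysis.
2. **Sample Size.** State the planned number of weeks and the expected patients per week. Replace the unqualified 80% with power at n=80 over an ICC range such as 0.01 to 0.10. Keep the sentence on finishing the last week, adding that further patients in the same week bring less power than independent patients would.

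The cost is wording in two sections and slightly more analysis work. No extra enrolment is needed to make the change. The stated power becomes less favourable: the change discloses the shortfall and does not by itself restore 80%.

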### **Interventions and Interactions**

Patients scheduled for office intra-detrusor chemodenervation will be contacted by study staff via phone to introduce the study and gauge interest in participating. Interested and eligible patients will be asked to arrive thirty minutes before their scheduled procedure time to complete the consent process. Upon arrival, patients will be escorted to a research office where informed consent will be obtained. After obtaining informed consent, all participants will fill out a pre-procedure visual analog scale (VAS) for

anxiety (Figure 1) and a VAS for pain (Figure 2). If all inclusion criteria are met, including VAS-anxiety  $\geq 12$ mm on 100mm scale, participants will be enrolled and then escorted to the procedure room.

### **Intervention:**

#### **Group 1:** Intervention

- Lavender aromatherapy sticker on patient, procedure staff, MD lapel
- Calming music from Sirius XM station 68 (Spa) playing via overhead speakers
- Overhead lights off, two lanterns lit to provide dim lighting
- Avoid stirrup use

#### **Group 2:** Control

- Non-aromatic (placebo) sticker on patient, procedure staff, MD lapel
- No music playing
- Overhead lights on
- Stirrups used

In order to create the least disruption to our clinical workflow, we propose randomizing the weeks of the study rather than randomizing participants. Permuted block randomization will be used such that a random sequence of blocks of 4 or 6 weeks (totaling to the number of weeks planned for the study) will be chosen. Within each block of 4 or 6 weeks, the weeks will be equally randomized to treatment or control. For example, within a four-week block, two of four weeks will be randomized treatment and two to control. Permuted block randomization will ensure that (i) prognostic factors (e.g., first-time vs. repeat patient) are balanced over the course of the study and (ii) seasonality is addressed (e.g., within summer, half of the weeks are control and half treatment). Each week of the study will be randomized to either Relaxing Environment Package or Typical Office Environment (control), rather than randomizing individual patients. On Monday of every week, an envelope will be opened to determine if it is a Relaxing Environment Package week or Control week. Randomization will be discussed in more detail below.

If the week is randomized to a *Relaxing Environment Package*, the patient, procedure staff, and MD will enter the procedure room and receive a lavender aromatherapy sticker to be worn on their lapels. The lavender aromatherapy sticker will be ordered from Aroma Stickers store website (<https://aroma-stickers.com>). Calming music from Sirius XM station 68 (Spa) will be playing softly in the background via overhead speakers. If the patient had planned to listen to their own music during the procedure, this will be permitted and documented. Procedure consent and preprocedural preparation (see below) will take place. The overhead lights will then be turned off, and two battery powered lanterns will be lit to provide dim lighting. Stirrups will be avoided, if possible, during the preparation and procedure.

If the week is randomized to *Typical Office Environment*, the patient, procedure staff, and MD will enter the procedure room and receive a non-aromatic (placebo) sticker to be worn on their lapels. The non-aromatic sticker will be obtained from an office supply store. No music will be playing, and all of the lights will be on as is typical in our practice. Procedure consent and preprocedural preparation (see below) will take place. The lights may then be adjusted during cystoscopy per provider preference for adequate visualization.

To minimize lavender cross contamination and unintended topical or environmental exposure in those not participating in the study or with lavender allergy, we opted to use a lavender aromatherapy sticker rather than a diffuser. Unlike a diffuser, the aromatic sticker does not leave a scent in the air once the sticker is removed from the room. When the aromatic sticker is worn on a shirt lapel it can only be smelled at close distances, typically only by the individual wearing the sticker. Aromatic stickers will be maintained outside the procedure room in a sealed bag. If a patient is randomized to the Relaxing Environment Package, the stickers will be brought into the procedure room and distributed to patients and staff. The sticker will be placed on the subjects' shirt lapel. Once the procedure is completed the stickers will be recollected, placed back in the sealed bag, and disposed of by study staff. This will limit any environmental exposure to lavender for the next patient. Routine hand washing or sanitization by MD and procedure staff and routine cleaning of procedure room between patient encounters will limit any cross contamination or unintended topical exposure. For patients or staff not participating, we believe that lavender levels will not be above those expected in everyday life. Additionally, our office has a second procedure room that can be used for any patients with a lavender allergy.

All patients will receive routine preprocedural antibiotic prophylaxis, sterile urethral preparation with betadine or chlorhexidine, and 60cc viscous intravesical 1% lidocaine will be instilled into the bladder with sterile technique. After staying in the environment in the supine position with a sheet covering the lower half of their body and legs for at least 10 minutes while the local anesthetic takes effect, participants will then fill out a 2nd VAS for anxiety. The procedure will be performed, and any patient requested modifications to the protocol will be recorded. After the procedure and once participants are dressed, they will fill out a 2nd VAS for pain and a VAS for procedure satisfaction (Figure 3).

The procedure staff and MD will fill out the Burnout Battery visual analog scale (Figure 4) at the start of the day prior to seeing any patients. They will again complete the Burnout Battery visual analog scale at the day's conclusion, after seeing their last patient. They will also record how many chemodenervation procedures they participated in that day.

The electronic medical record, with participant permission, will be reviewed to establish patient demographics, indication for procedure, whether primary or repeat procedure, and medical history. Years of experience and demographic information of the procedure staff and MD will also be recorded.

	Baseline	Procedure	Post-procedure
Informed Consent	x		
Medical History	x		
Medication review	x		
*Other Demographics	x		
VAS Anxiety #1	x		
VAS Pain #1	x		
Randomization	x		
VAS Anxiety #2		x	
**Procedure		x	

VAS Pain #2			x
VAS Patient Satisfaction			x

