**Table 1. Patient Data Collection Schedule**

\*Other demographic data includes: Age (years), Race, Body Mass Index (BMI in kg/m^2), smoking status (current/former/never), insurance type (private/Medicare/Medicaid/None), use of aromatherapy at home in the last six months (yes/no)

\*\*Procedure data includes: first time injection (yes/no), repeat procedure (yes/no), time of patient entering room, time of VAS anxiety #2, protocol modifications (stirrups used, support person present, listening to personal music, other relaxation techniques used, etc)

	Baseline	Start of clinic day	End of clinic day
Informed Consent	x		
*Demographics	x		
Burnout Battery		x	x

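### Blocking weeks does not ensure balance on first-time versus repeat status, yet adjustment for that factor in the primary model is left open

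*Combined protocol and SAP*

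**What the plan says.** The text after Group 2: Control explains the allocation: "we propose randomizing the weeks of the study rather than randomizing participants". For the blocks, "a random sequence of blocks of 4 or 6 weeks (totaling to the number of weeks planned for the study) will be chosen", and within each block "the weeks will be equally randomized to treatment or control". The Randomization section repeats this: "A permuted block randomization scheme will be used to assign weeks in a 1:1 ratio to intervention or control".

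Two benefits are claimed. The first is "Permuted block randomization will ensure that (i) prognostic factors (e.g., first-time vs. repeat patient) are balanced over the course of the study". The second is that "seasonality is addressed (e.g., within summer, half of the weeks are control and half treatment".

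The Analytical Plan tests treatment effects by regression. It says that the models can "include covariate adjustment for important prognostic variables (such as first-time vs. repeat patient), as necessary". It does not define when adjustment is necessary. The factor is recorded for every patient: the notes to Table 1 list "first time injection (yes/no), repeat procedure (yes/no".

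**The concern.** The second claimed benefit is what blocking by week delivers: each arm gets its share of weeks in each stretch of the calendar. The first does not follow. No stratification, minimisation or other constraint uses first-time or repeat status, and the clinic schedule decides who attends in a given week.

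The same variable is the plan's own example of an important prognostic factor, and whether it enters the primary model is undecided. With no rule, the analysis could be settled after the split between arms, or the result, is known. There are then two candidate primary answers, and a reader of the report could not tell whether the one shown was planned.

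**Working it through.** **The plan's own figure.** Inputs from the Sample Size section: difference 12 mm, SD 18.8 mm, 80% power, 0.05 level (taken as two-sided). n per arm = 2 × (1.960 + 0.842)² × 18.8² / 12² = 38.5, so 39 per arm or 78 in all. The t-test gives 79.5% power at 39/39 and 80.5% at 40/40, so n = 80 is reproduced for equal arms and independent patients. The planned standard error of the difference is 18.8 × √(2/40) = 4.2 mm.

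**What the scheme constrains.** Completed blocks hold equal numbers of weeks per arm. Enrolment stops at the end of the week in which 80 is reached, which may fall inside a block, so even week counts can differ, by at most 3 (half of the largest block). Nothing constrains patient type.

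**Benchmark: unstratified randomisation of patients, 40 per arm.** With half first-time (assumption), the standard error of the difference in first-time share is √(0.5 × 0.5 × 2/40) = 0.112. The median absolute gap is 0.674 × 0.112, or 7.5 points. The chance of a gap of 15 points or more is 2 × P(Z > 0.15/0.112) = 18%.

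**Simulation of the weekly scheme.** Blocks of 4 or 6 weeks and stopping after the week that reaches 80 come from the protocol. The rest is assumed, because the documents give no values: 2, 4 or 8 patients per week on average, week sizes Poisson or more variable (extra CV 0.4), first-time share 30% or 50%, and an intraclass correlation (ICC) of first-time status within weeks of 0 or 0.05. Each setting was run 4,000 times.

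| Design | Gap ≥10 points | Gap ≥15 points | Gap ≥20 points |
|---|---|---|---|
| Patients randomised, half first-time | 37% | 18% | 7% |
| Weeks in blocks, half first-time, ICC 0 | 36–38% | 17–19% | 7–8% |
| Weeks in blocks, half first-time, ICC 0.05 | 38–46% | 20–26% | 9–13% |
| Weeks in blocks, 30% first-time, ICC 0 | 32–34% | 13–15% | 4–5% |
| Weeks in blocks, 30% first-time, ICC 0.05 | 35–41% | 16–22% | 6–10% |

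Separate runs with half first-time gave a gap of 15 points or more in 17–18% of trials at ICC 0 and in 21–24% at ICC 0.05. The slightly wider ranges in the table reflect the more variable week sizes and simulation error. At ICC 0 the median gap is about 7.5 points; at ICC 0.05 it is about 8–9 points.

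**Effect on the estimate.** Shift = (difference in mean anxiety change between first-time and repeat patients) × (gap in first-time share). With an assumed difference of 5–10 mm:

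- Median gap: 0.075 × 5 = 0.4 mm to 0.075 × 10 = 0.75 mm, or 3–6% of 12 mm.
- 20-point gap: 0.20 × 5 = 1 mm to 0.20 × 10 = 2 mm, or 8–17% of 12 mm and about a quarter to a half of the 4.2 mm standard error.

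**Precision from adjusting.** The variance explained is 0.25 × 5² / 18.8² = 2% to 0.25 × 10² / 18.8² = 7%, which cuts the standard error by about 1–4%.

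**The case against.** Five points on the other side deserve weight.

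- Blocking does more than count weeks. It spreads both arms over the calendar and so protects against drift in patient mix. The simulations hold the first-time share constant and do not test this. That stands, but protection against drift is not assurance of balance.
- The imbalance is ordinary chance. It does not bias a randomised comparison in expectation, and the standard error already allows for it. This stands. A reader might infer that the trial is biased by it; the documents do not support that.
- The shift is small. The 1–2 mm figure needs a 20-point gap, which occurs in 4–13% of simulated trials, and an assumed prognostic difference. The outcome is change from baseline, so any part of first-time status that only raises the starting level is already subtracted. This stands and limits the weight of the point.
- A reader might infer that the plan also promises equal numbers of patients per arm. It does not: the 1:1 ratio is stated for weeks only. Unequal arms would in any case cost little, with t-test power of 80.5% at 40/40 and 77.9% at 50/30.
- A reader might infer that adjustment was made optional because balance was taken for granted. The Analytical Plan draws no such link.

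The plan does name the factor for baseline summary, adjustment and subgroup analysis, and its statistician is to be blinded. That lowers the risk of a result-driven choice but does not replace a stated rule.

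**Conclusion.** The balance claim is wrong as worded: the design equalises weeks, not patient types, and does about as well on first-time status as unstratified randomisation of patients, or somewhat worse if patient types cluster by week. A gap of 15 points or more would arise in about 17–24% of trials with half first-time patients and 2–8 enrolled per week. The likely effect on the estimate is modest: 0.4–0.75 mm at the median gap and 1–2 mm at an uncommon one. Weekly volume, first-time share, ICC and the 5–10 mm prognostic difference are all assumptions.

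The case for change therefore rests less on the size of the shift than on two facts that need no assumption: the protocol states a property that the design lacks, and the primary model is left open on the very factor that the plan calls important.

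**What to change.** In the randomisation text after Group 2: Control, replace the claim about prognostic factors with a statement that blocking balances the number of weeks per arm over calendar time, exactly so only in completed blocks.

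In the Analytical Plan, delete the qualifier *as necessary*. State that the primary model for change in VAS anxiety includes first-time/repeat status and baseline VAS anxiety in all cases, and accounts for week as the randomised unit. Fix this before any outcome data are examined. An unadjusted result may be reported as supportive.

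The cost is wording only, with no new data: both covariates are already collected and the stated n = 80 does not change on their account. The two covariates use two degrees of freedom. Accounting for week costs more. At 2, 4 or 8 patients per week, 80 patients span about 40, 20 or 10 weeks, so a week-level comparison of two arms has about 38, 18 or 8 degrees of freedom, and the interval may be wider. That follows from randomising weeks, not from adjusting for first-time status.
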